11.1.6 Duration of Response

Duration of overall response: The duration of overall response is measured from the time measurement criteria are met for CR/PR or iCR/iPR (whichever is first recorded) until the first date that recurrent or progressive disease is objectively documented (taking as reference for progressive disease the smallest measurements recorded since the treatment started).

The duration of overall CR is measured from the time measurement criteria are first met for CR until the first date that progressive disease is objectively documented.

Duration of stable disease: SD is measured from the start of the treatment until the criteria for progression are met, taking as reference the smallest measurements recorded since the treatment started, including the baseline measurements.

11.1.7 *Progression-Free Survival*

PFS is defined as the duration of time from start of treatment to time of progression or death, whichever occurs first.

11.1.8 *Response Review*

Radiological images will be collected for a possible review of response by an expert(s) independent of the study. Measurement of tumor response by a trained radiologist/nuclear medicine physician at each clinical site will be chronicled and reported unless or until a central expert review takes place.

11.2 Correlative Studies

11.2.1 *Integrated Correlative Studies Background*

11.2.1.1 *Evaluation of Peripheral CD4+ and CD8+ T-cell Counts – Integrated Laboratory Correlative Study #1*

As described above, NT-I7 has been shown to double the number of peripheral blood lymphocytes including T-cells. Thus, CD4+ and CD8+ T-cell numbers are important biomarkers for the effect of NT-I7 on the peripheral T-cell populations. To assess the overall pharmacodynamic effect of atezolizumab plus NT-I7 and to determine whether NT-I7 in combination with atezolizumab results in the same, or different, level of expansion of peripheral lymphocytes, T-cell counts (both CD4+ and CD8+) will be evaluated in Clinical Laboratory Improvement Amendments (CLIA)-certified laboratories locally at each site. CD4+ and CD8+ T-cell counts will be evaluated at baseline, during treatment, and at end of therapy.

Hypothesis: The combination of atezolizumab with NT-I7 will result in similar levels of peripheral blood T-cell expansion as with NT-I7 alone.

11.2.1.2 *Slide-Based Immune Phenotype Panel -- Multispectral IHC – Integrated Laboratory Correlative Study #2*

Because tumor-infiltrating immune cells are associated with clinical outcomes, infiltrates from pre-treatment tumor tissue and from biopsies taken during treatment will be assessed by immunohistochemistry (IHC) to determine extent and the nature of T-cell infiltration and of the overall immune milieu of the TME.

Paired baseline and post-baseline tumor biopsies will be evaluated using quantitative multicolor IHC with Perkin-Elmer's Vectra IHC platform. This platform employs spectral deconvolution imaging to separate optical signals from each antibody together with state-of-the-art image analysis capabilities to facilitate robust quantitative slide-based immunophenotyping. Using the

Vectra multispectral imaging platform (PerkinElmer), adjacent tumor sections will be stained and imaged with a series of 5-6 antibodies per section simultaneously to investigate the spatial relationship between key immunomodulatory cell types and molecules. The antibodies will include but are not limited to the following: pancytokeratin (AE1/AE3), CD8+, CD4+, PD-1, PD-L1, CD68, CD163, FOXP3, arginase, and pan- major histocompatibility complex (MHC) class I and class II. Data will be generated in the form of total positive cells, positive cells/mm², percentage positive cells in a population, ratios of cells and molecules of interest (e.g., PD-L1:CD8+ or FOXP3+CD4+:CD8+). Additionally, tumors may also be assayed by IHC for a variety of other markers including CD80, IFN- γ CD3, CD5, TIA-1, CD20, CD11b, CD137, CD45RO, CD301CD56 and CD16 (NK and NK T-cells), CD79a (B cells), GITR, TIM-3, FOXP3, LAG3. Furthermore, quantitative analysis of tumor-infiltrating lymphocyte (TIL) distribution (i.e., stromal and interface/invasive margin) will be performed. Anti-PD-L1 immunohistochemical staining with the SP142 PD-L1 clone (IHC assay, HistoGeneX/CellCarta) kit will be performed in addition to the multispectral IHC (msIHC) to serve as both an independent test and control for the reproducibility of the msIHC assay. The study is intended to evaluate for changes in the immune profile of the TME. If sufficient archival tumor tissue collected before therapy is not available, a baseline biopsy will be obtained before enrolling in the study as part of this protocol.

IHC studies will be performed at the Fred Hutchinson Cancer Center (Fred Hutch) Immunopathology Laboratory, Seattle, WA, or other agreed upon investigator.

Hypothesis: The combination of atezolizumab with NT-I7 will alter the TME toward a pro-inflammatory phenotype.

11.2.1.3 *Assessment of Tumor Biopsy by Gene Expression Analysis -- Interferon γ (IFN γ) Gene Expression Signature - NanoString[®] PanCancer IO 360TM Gene Expression Panel and the nCounter[®] PanCancer Immune Profiling Panel – Integrated Laboratory Correlative Study #3*

To identify potential signatures correlating with tumor T-cell infiltration patterns and clinical response, tumor tissue will be tested for gene expression using NanoString[®] technology on unstained tissue formalin-fixed paraffin-embedded (FFPE) slide material. Specifically, slides will be analyzed using a 770-gene panel (nCounter[®] PanCancer Immune Profiling Panel), which contains markers for 24 different immune cell types and populations, 30 common cancer antigens and genes that represent immune responses including checkpoint blockade genes as well as the NanoString[®] nCounter[®] PanCancer IO 360TM Gene Expression Panel, which contain genes associated with the IFN γ Gene Expression Signature. These gene expression profiles may provide an additional detailed phenotype to guide correlative investigation.

NanoString[®]-based gene expression analysis, specifically for the IFN γ Signature, will be used to test the hypothesis that the investigational study treatment regimen, NT-I7 plus atezolizumab, will promote a proinflammatory antitumor immune response. The IFN γ Signature, which is comprised of IDO1, CXCL10, CXCL9, HLA-DRA, STAT1 and IFN γ , has previously been shown to correlate with anti-PD-1 response and nonresponse. RNA will be extracted from all paraffin-embedded tumor samples and analyzed using the aforementioned NanoString[®] nCounter technology or similar panels. The samples used will be taken from tissue sections adjacent to

those stained for mIHC to facilitate comparison between these analysis sets. Samples will consist of matched pre- and post-treatment FFPE biopsies.

These analyses will be performed in coordination with NanoString® Technologies in Seattle, WA, and analyzed using qualified analytic tools at the Immunopathology Lab at Fred Hutch.

Hypothesis: The combination of atezolizumab with NT-I7 will alter the TME toward a pro-inflammatory gene expression programming (GEP) phenotype, and distinct gene expression patterns will be identified that may correlate with clinical outcomes.

11.2.1.4 *T-Cell Receptor Repertoire Analysis -- TCR sequencing – Integrated Laboratory Correlative Study #4*

We will perform TCR sequencing where pre-treatment and post-treatment biopsies are available. TCR repertoire analysis will be performed on RNA extracted from FFPE biopsies and T-cells isolated from peripheral blood mononuclear cells (PBMCs) collected throughout study participation. TCR repertoire analysis has been standardized and commercialized by Adaptive Biosciences. The TCR sequences will also specifically be queried for sequences already known to encode for TCRs reactive to shared antigens in the particular tumors, such as MCC virus in virus positive MCC.

Samples will be analyzed at Adaptive Bioscience in Seattle, WA, or other agreed upon vendor or collaborator.

Hypothesis: The combination of atezolizumab with NT-I7 will: i) result in emergence and/or increased prevalence of specific TCR sequences reflecting the clonal expansion of antitumor T-cells; and ii) expansion of those specific T-cell clones in TILs (exhibited by higher TCR clonality) will be associated with improved response to therapy.

11.2.1.5 *Tumor-Associated Neo-antigen Discovery -- Whole Exome Sequencing (WES) and RNAseq and Antigen Prediction – Integrated Laboratory Correlative Study #5*

In order to investigate the role of T-cell-mediated immunity directed toward tumor-specific mutant antigens, whole exome sequencing (WES) and RNAseq of tumor cells from baseline tumor biopsy relative to non-tumor cells from whole blood (PBMC) will be performed to: i) identify tumor-associated neoantigens; and ii) identify the genomic variances that may contribute to response or disease progression and provide an understanding of molecular abnormalities.

DNA and RNA will be extracted from baseline or archival FFPE tumor biopsies and then sequenced to identify overexpressed, known “shared” tumor-associated antigens (TAAs) and nonsynonymous expressed mutations using available and standard-of-practice technologies. For example, a computational approach (BIMAS and SYFPEITHI algorithms) can be utilized to analyze and prioritize these mutation-derived “virtual” antigens in terms of their likelihood to bind to/be presented by relevant MHC I alleles. Potential antigens can be encoded in tandem minigene constructs with intervening P2A viral sequences to allow for equimolar expression of multiple “long” (~27 amino acids) peptides centered on the putative antigenic mutational sites. These neoantigen libraries will be cloned into an appropriate expression vector to allow for in vitro-transcription of neoantigen-encoding mRNA for use in enzyme-linked immunospot (ELISPOT) assays to detect neoantigen immune responses. RNAseq will also identify whether

common “shared” antigens are also expressed. Quantitation of mutation burden may also be important for urothelial carcinoma, where immunogenicity and/or responses to PD-1/PD-L1 axis-directed therapies may be associated with a high mutation burden.

These analyses will be performed using qualified analytes and analytic tools at the Immunopathology Lab at Fred Hutch or at a vendor, to be determined.

Hypothesis: Clinical outcomes will correlate with mutational burden, and tumor-associated neoantigens will be identified that correlate with T-cell responses and clinical outcome.

11.2.1.6 *Antitumor Immune T-cell Responses – ELISPOT – Integrated Laboratory Correlative Study #6*

If there are positive clinical responses, antigen-specific T-cell responses may be assessed by IFN γ ELISPOT assay to provide information regarding the effect of the atezolizumab and NT-I7 regimen on antigen-specific T-cell functional antitumor responses such as MCC virus. The ability of the investigational treatment to induce a tumor antigen-specific immune response will be assessed using ex vivo incubation of PBMC-derived T-cells with autologous PBMC either pulsed with peptide antigens or recombinant proteins representing MCC virus or neoantigens described above. Memory viral responses (influenza A, Cytomegalovirus, Epstein-Barr Virus and Flu [CEF]) will also be assessed as controls. We will quantitate the strength of the antigen-specific T-cell responses and compare baseline and post-baseline T-cell responses for each putative antigen. The absolute change in ELISPOT responses for antigens will be compared between the spot-forming cells (SFC)/million PBMC at baseline (before treatment initiation) and at designated time points post-treatment.

Assays will be performed in the Central Immune Monitoring Laboratory (CIML) at the Fred Hutch, or an agreed upon vendor or collaborator.

Hypothesis: The combination of atezolizumab with NT-I7 will result in increased T-cell responses to known and/or neoantigens.

11.2.2 *Exploratory/Ancillary Correlative Studies*

11.2.2.1 *Assessment of PD-L1 Expression at Baseline and Post-treatment -- Immunohistochemistry (IHC) – Exploratory Laboratory Correlative Study #1*

PD-L1 has been identified as an important correlative biomarker for clinical response to anti-PD-L1 and anti-PD-1 therapies. In particular, given that the function of atezolizumab is to block binding of PD-1 to PD-L1, expression of PD-L1 will be quantitated by IHC in baseline FFPE tumor specimens, and from biopsies obtained after treatment. This is an important part of the correlative studies to explore whether this marker which correlates with response in other circumstances also correlates with response in this protocol population. For baseline samples, FFPE tissue block(s) from tumor obtained before treatment will be obtained by the clinical site either from archival samples obtained from the relevant pathology laboratories where they were processed and stored, or from baseline biopsy as part of this protocol (core biopsy, punch biopsy or surgical excision). Post-treatment, FFPE tumor specimens will be obtained from biopsy at Cycle 2 (core biopsy, punch biopsy or surgical excision) as part of this protocol.

PD-L1 expression will be tested by IHC at HistoGeneX/CellCarta with the SP142 PD-L1 clone or other agreed upon vendor.

Hypothesis: PD-L1 expression at baseline will correlate with clinical responses to atezolizumab and atezolizumab in combination with NT-I7. In addition, atezolizumab administration may alter PD-L1 expression to an unknown extent.

11.2.2.2 *Evaluation of the Effect of Atezolizumab with and without NT-I7 on Circulating Lymphocyte and Monocyte Numbers and Phenotype – Exploratory Laboratory Correlative Study #2*

We will assess the effects of the atezolizumab with and without NT-I7 on the frequency and phenotypic character of PBMC subsets including dendritic cells (DCs), monocyte populations, T-cells, NK cells, and B cells. The effect on these immune cell subtypes of checkpoint inhibitors and other immune modulators is being investigated in other CITN trials and may provide important correlative information on the success or failure of combination immunotherapy.

A 21-color whole blood immunophenotyping assay will quantify in 1 panel the absolute number and proportion of T-cells (both CD8+ and CD4+), NK cells (CD56+CD3-), NKT-cells (CD56+CD3+), B cells (CD19+), monocytes (CD16+), as well as both myeloid DCs (CD45+HLA-DR+CD11c+CD123-) and plasmacytoid DCs (CD45+HLA-DR+CD11c-CD123+). In addition, to further define the phenotype and activation status of T-cells, the panel includes memory markers (CD45RA, CD197 [CCR7]), activation and Treg markers (CD28, CD127, CD25, HLA-DR, CD279 [PD-1]), and markers of exhaustion (Lag-3, Tim-3, TIGIT).

Additional whole blood immunophenotyping assays will assess the Treg population in a FoxP3 flow assay (CD45, CD3, CD4, CD25, CD127 and FoxP3) and proliferating levels of several cell subsets in a Ki67 assay (CD3, CD4, CD8, CD14, CD56 and Ki67).

For the expansion cohort, we also use a 13-color whole blood immunophenotyping assay to further quantify T cell differentiation subsets such as T_N (CD45RA+CCR7+CD95-CD127+), T_{SCM} (CD45RA+CCR7+CD95+CD127+), T_{CM} (CD45RA-CCR7+CD95+CD127+), T_{EM} (CD45RA-CCR7-CD95+CD127+/-), T_{TE} (CD45RA+CCR7-CD95+CD127-), and “Stem-like” CD8 T_{SL} (CD8+PD-1+CXCR5+TIM-3-) and exhausted T_{SL} (CD8+PD-1+CXCR5-TIM-3+).

Assays will be performed in the CIML at the Fred Hutch.

Hypothesis: The combination of atezolizumab with NT-I7 will perturb circulating lymphocyte and monocyte numbers and phenotypes to a yet unknown extent.

11.2.2.3 *Multiplex Cytokines– Exploratory Laboratory Correlative Study #3*

Perturbations in cytokines, chemokines, and growth factors have been associated with cancers and changes in plasma cytokine concentrations of proinflammatory and immunosuppressive cytokines may correlate with clinical responses to therapy. Measurable changes in serum and plasma cytokines have been associated with checkpoint blockade therapies. Comparison of baseline plasma cytokines, chemokines and growth factors to longitudinal measurements during therapy may improve our understanding of the immunologic effects of the combination of atezolizumab plus NT-I7 on cancer. Furthermore, these assays will be used to explore whether

reactive changes in cytokine levels correlates with toxicity and/or efficacy of atezolizumab and NT-I7. Longitudinally collected plasma samples will be evaluated using commercial multiplex immunoassays (i.e., Luminex) or other appropriate technology (i.e., Olink primer extension assay) for quantitation.

Assays will be performed at the Fred Hutch Shared Resources, or at other agreed upon vendor.

Hypothesis: The combination of atezolizumab with NT-I7 will perturb cytokines, chemokines, and growth factors to a yet unknown extent.

11.2.2.4 *Kynurenine and Tryptophan (Kyn/Trp) Ratios and Plasma Arginine Levels – Exploratory Laboratory Correlative Study #4*

Over expression of IDO is known to result in increases in the kynurenine and tryptophan (Kyn/Trp) ratio in blood and within some TMEs. Increases in Kyn/Trp ratios result in the subsequent suppression of T-cell responses and is a major mechanism of immune control. IDO is expressed by some tumors, but probably more importantly, it is expressed by lymphocytes as a normal mechanism and important mechanism to dampen immune responses. Expression of IDO (with subsequent increased Kyn/Trp ratios) may be one likely mechanism of checkpoint blockade and other immunotherapy failures. Thus, we will measure Kyn/Trp ratios in plasma taken at baseline, during treatment and at end of treatment to analyze, in patients who have failed clinical response to atezolizumab plus IL-7 treatment, whether failure may be associated with increased Kyn/Trp levels.

In addition, another important mechanism of immune control and suppression is through changing concentrations of arginine (Arg) insofar as decreased levels of Arg in plasma (i.e. ARG depletion) is associated with decreases in CD4+ and CD8+ T-cell proliferation and decreased Th1 functions. Arg depletion can occur by the release by myeloid-derived suppressor cells (MDSCs) of arginase which converts L-Arg to ornithine. This may be another mechanism of tumor evasion as myeloid suppressor cells with high arginase activity are found in tumors. Thus, we will also measure Arg levels in the same plasma samples taken at baseline, during treatment and at end of treatment in this protocol to analyze, in patients who have failed clinical response to atezolizumab plus IL-7 treatment, whether failure may be associated with increased Arg levels in plasma.

All assays will be performed at an agreed upon collaborator or vendor to be determined.

Hypothesis: Failure to respond to atezolizumab plus NT-I7 treatment may be associated with increased Kyn/Trp ratios and/or increased plasma Arg levels in some patients.

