Scheduling Window	Within 14 days	Day 1	Day 2	Day 8± 2 days	Day 1± 2 days	Day 8± 2 days	Day 1± 2 days	Day 8± 2 days	Day 1± 2 days	Day 8± 2 days	Day 1± 2 days	Day 8± 2 days	Day 1± 2 days	Day 8± 2 days	Day 1± 2 days	Day 8± 2 days	30 days ± 5 days post Tx	60 and 90 days ± 7 days post Tx	Every 12 wks ± 1 wk	Every 12 wks ± 1 wk
Efficacy Measurements																				
Tumor measurements	Within 28 days	Tumor measurements are performed at 9 weeks ± 1 week for the first two timepoints, then every 12 weeks ± 1 week . Documentation (radiologic) must be provided for patients removed from study for progressive disease.														X ⁱ		X		
Radiologic evaluation	Within 28 days	Radiologic measurements should be performed at 9 weeks ± 1 week for the first two timepoints, then every 12 weeks ± 1 week														X ⁱ		X		
Tumor Biopsies/Archival Tissue Collection																				
Tumor Biopsy	X ^d					X ^d														
Correlative Studies Blood Draws^e																				
T-cell count (CD4/CD8)		X ^e			X ^e		X ^e		X ^e	X ^e	X ^e									
Pharmacokinetics ^h		X	X ^{**}	X			X			X					X					
Immunophenotyping		X		X ^k	X		X	X	X	X					X					
Multiplex Cytokines		X			X		X		X	X					X					
TCR sequencing		X			X		X		X	X										
ELISPOT		X			X		X		X	X										
Kyn/Trp and Arginine		X			X		X		X	X					X					
Immunogenicity Testing ^j (NT-I7)		X			X		X		X	X			X	X	X		X ⁱ			

A NT-I7: Dose as assigned; starting with DL4 (1200 µg/kg), NT-I7 dosing is changed from Q3W to Q6W (i.e., Cycle 1, Day 1, Cycle 3, Day 1, Cycle 5, Day 1, etc.). NT-I7 will be skipped when the ALC is higher than 10,000 cells/µL on Day 1 of each cycle, starting on Cycle 3 (protocol Section 5.2).

* NT-I7 must be administered 60 (± 10) minutes before atezolizumab.

B Atezolizumab: Dose as assigned; once every 3 weeks, starting Cycle 1, Day 1.

a Vital signs assessment before and after study treatment is required (Section 6.1.1 and 6.1.2).

b Albumin, alkaline phosphatase, total bilirubin, bicarbonate, BUN, calcium, chloride, creatinine, glucose, LDH, phosphorus, potassium, total protein, SGOT [AST], SGPT [ALT], lipase, amylase, TSH and sodium.

c Pregnancy test (women of childbearing potential) must be performed within 72 hours prior to initiation of study treatment per eligibility criteria and at the 90-day Safety Follow up visit.

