15.5.2 Exploratory Endpoints

Statistical analyses will be conducted to determine the immune correlates of the clinical activity of the investigational treatment combination.

The endpoints will include the evaluation of the effect of the investigational treatment combination on the immune-bias of the TME, based upon baseline and post-baseline tumor biopsy comparisons of:

- Serum concentration of NT-I7 administered in combination with atezolizumab at specified timepoints for the following parameters: Area under the concentration time-curve (AUC), maximum serum concentration (C_{max}), minimum serum concentration (C_{min}), Clearance (CL)
- Number, distribution, and phenotype of tumor-infiltrating cells
- PD-L1 expression
- Expression of IFN γ and associated proinflammatory gene expression in the TME
- Changes in TME that correlate with response or provide information on potential actionable causes for lack of clinical benefit.

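### The Kyn/Trp and arginine analysis is stated only in patients who failed treatment, a set in which no association with failure can be estimated; it needs a comparison with responders

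*Protocol*

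**What the plan says.** Protocol Section 11.2.2.4 (Exploratory Laboratory Correlative Study #4) gives the aim once per marker. For Kyn/Trp it is "to analyze, in patients who have failed clinical response to atezolizumab plus IL-7 treatment, whether failure may be associated with increased Kyn/Trp levels". For arginine the analysis is "in patients who have failed clinical response to atezolizumab plus IL-7 treatment, whether failure may be associated with increased Arg levels in plasma". The hypothesis that closes the section has no such restriction: "Failure to respond to atezolizumab plus NT-I7 treatment may be associated with increased Kyn/Trp ratios and/or increased plasma Arg levels in some patients".

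Measurement is not restricted either. The section says "we will measure Kyn/Trp ratios in plasma taken at baseline, during treatment and at end of treatment", and the row "Kyn/Trp and Arginine" in the Section 10 calendar, which covers both arms, schedules draws on Day 1 of Cycles 1, 2 and 3 and at later visits, whatever the response.

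Elsewhere, Protocol Section 15.5.2 says only that "Statistical analyses will be conducted to determine the immune correlates of the clinical activity of the investigational treatment combination". Its list covers serum NT-I7 and tumour-biopsy endpoints, not plasma Kyn/Trp or arginine. The SAP shows the assay in its schedule, plans no analysis of it, and in Section 2.5.2 leaves correlation of pharmacodynamic with efficacy parameters outside its scope.

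**The concern.** An association between failure and a marker is a contrast between patients who failed and patients who did not. If only failures are analysed, response status is constant and the contrast does not exist. What remains is the marker's level in failures, or its course over the serial samples. That answers a different question: whether the marker moves in patients who failed.

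The two questions separate when the regimen itself moves the marker. The protocol's own biology makes this plausible. Section 11.2.2.4 says that lymphocytes express IDO as a normal brake on immune responses, and Section 11.2.1.1 says that NT-I7 has been shown to double peripheral lymphocyte numbers. A Kyn/Trp rise in all treated patients is therefore credible. Seen only in failures, it would look like support for IDO as a reason for treatment failure.

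The neighbouring studies are not framed this way. Section 11.2.2.1 asks whether PD-L1 correlates with response in the protocol population, and Section 11.2.2.3 asks whether cytokine changes correlate with toxicity or efficacy.

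**Working it through.** **No plan figure to reproduce.** The documents attach no sample size, alpha, effect size or test to this analysis. The main point is logical and needs no arithmetic. The figures below only show its possible size.

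**Inputs.** Phase 2a has 24 patients in Arm I and 36 in Arm II; the historical response rates are 45.25% and less than 5% (Protocol Sections 15.2.2 and 15.3).
- Arm I: 24 × 0.4525 = 10.9, taken as 11 responders and 13 failures.
- Arm II: 36 × 0.05 = 1.8, taken as 2 responders and 34 failures.
- Together: 13 responders and 47 failures.

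Assumed: complete samples, normally distributed changes in SD units, two-sided 5% t-tests, and every non-responder counted as a failure. Section 15.6.2 treats stable disease as outside treatment failure, so the failure set could be smaller; 30 and 20 are shown as well.

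**A rise of d SD in everyone, unrelated to response.** A one-sample test of change in n failures has noncentrality d√n.
- n = 47, d = 0.3: 0.3 × 6.856 = 2.06 against a critical value of 2.01; significant in 52%.
- n = 47, d = 0.5: 0.5 × 6.856 = 3.43; significant in 92%.
- n = 30: 36% and 75%.
- n = 20: 25% and 56%.

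In a responder versus non-responder comparison the common rise cancels, so the rate stays at 5%.

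**What the comparison can detect.** With a responders and b failures the noncentrality is d√(ab/(a+b)). At d = 0.8:
- Arm I (11 vs 13): 0.8 × √(143/24) = 1.95 against 2.07; power 46%.
- Arm II (2 vs 34): 0.8 × √(68/36) = 1.10 against 2.03; power 19%.
- Arms pooled (13 vs 47): 0.8 × √(611/60) = 2.55 against 2.00; power 71%.

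The 95% interval half-width is t × √(1/a + 1/b): 2.074 × 0.410 = 0.85 SD in Arm I and 2.032 × 0.728 = 1.48 SD in Arm II.

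**Why not simply pool.** Arm I supplies 11 of the 13 responders but only 13 of the 47 failures. If the marker's change differs between arms by 0.5 SD, with no link to response within either arm, the pooled difference is biased by 0.5 × (11/13 − 13/47) = 0.28 SD. By simulation the unadjusted pooled test is then significant in about 14% of trials, and in about 26% if the arms differ by 0.8 SD.

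**The case against.** The strongest reply is that the section is loosely worded rather than wrongly planned. Samples are scheduled in all patients, the hypothesis sentence is unrestricted, and Section 15.5.2 and the exploratory objective on predictors of anti-tumour activity both imply looking at responders. Describing which failures have raised Kyn/Trp is also a reasonable descriptive aim, and the hypothesis itself speaks only of some patients.

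Much of this stands. A reader might infer that responder samples will go unassayed; nothing in Section 11.2.2.4 or 12.2.4 says so. A reader might also take 52% and 92% as error rates of the protocol's analysis. They are not: no test is named, and SAP Section 4.2.5 says that no p-values will be reported. Nor does the failures-only set clearly miss a true hypothesis when responders fall and failures stay flat, because the hypothesis speaks of increased levels.

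What does not stand is that another section supplies the comparison. The only two analysis sentences for these markers both confine it to failures, and neither Section 15.5.2 nor the SAP names a responder contrast for plasma Kyn/Trp or arginine. A description within failures is useful, but it cannot show an association with failure.

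**Conclusion.** The point holds, at minor severity. The stated analysis set cannot answer the stated question for either marker, whatever statistic is used, and it leaves a treatment-wide change open to being read as a mechanism of failure. The illustrative 52% and 92% rest on an assumed change-from-baseline test, 47 failures and common rises of 0.3 and 0.5 SD. They fall with fewer failures or a smaller rise.

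The reach is limited. The study is exploratory and stands last of the three plasma/serum priorities in Protocol Section 12. Neither marker is among the endpoints in Table 2. It would go too far to infer a threat to the efficacy, safety or dose conclusions, since none of them uses these data. It would also go too far to expect a firm answer from the corrected comparison. SAP Section 5 reports premature closure and limited responses, so the 46% and 19% are probably optimistic.

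**What to change.** In Section 11.2.2.4, for both markers, replace the clause restricting the analysis to patients who failed with a comparison across all patients who have samples:
- Compare baseline level, and change from baseline at Cycle 2 Day 1 and Cycle 3 Day 1, between confirmed responders and non-responders. With 21-day cycles these visits fall nominally at days 22 and 43, before the first scheduled tumour assessment at week 9.
- Do this within arm, or adjusted for arm.
- Report differences with 95% confidence intervals. If Arm II has only one or two responders, show individual values and leave that arm descriptive.
- Keep end-of-treatment values descriptive, because the timing of that visit depends on when treatment fails.
- State whether stable disease counts as failure.

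The cost is one reworded clause per marker. Plasma is already scheduled in both arms, so no new draws are needed. The price is wide intervals, which show the real uncertainty. The same edit could reconcile a separate inconsistency: the rationale treats arginine depletion as suppressive, while the analysis and hypothesis look for increased arginine.
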